4.2 Analysis of the primary outcome

The analysis for comparing the counts between the control and the intervention arms will be done using a GLMM (*Ime4* package, *Imer* function in R) with Poisson distribution using log link function, where a cluster will be specified as a random factor (i.e. random intercept) and recruitment time by

QMS Form number: FM-06-02-	CONFIDENTIAL	Page 14 of 26
05/v2.0		

FIND	Statistical Analysis Plan		
Protocol number:	TB041-3/1-TAN / -MOZ		
Document version:	5.0	Document date:	11-JUL-2023

clinic will be specified as a random effect nested within each cluster (i.e. random intercept and random slope).

The analysis for comparing the proportions between the control and the intervention arms will be done using a GLMM (*Ime4* package, *Imer* function in R) with binomial distribution using logit link function, where a cluster will be specified as a random factor (i.e. random intercept).

The models will be adjusted for gender, age, HIV status, country, and asset index that is described below. In case of necessity, the models may be adjusted for the setting (i.e. urban, rural, peri-rural nesting the clusters), and site.

ORs will be estimated by calculating the exponent of the fixed-effect (i.e. arm) coefficients that are extracted from the models described above. 95% confidence intervals will be calculated using Wald method.

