We will estimate the health system cost per participant tested for TB on-site via the novel Molbio Truenat MTB/RIF platform versus the hub-and-spoke standard of care, predominantly off-site testing with Xpert MTB/RIF (Cepheid, Inc., Sunnyvale, CA, USA). These include cost for equipment, staffing, consumables, training, communication, and monitoring and evaluation. We will estimate ranges for health service delivery costs using trial expense reports, facility assessments, and project staff interviews. We will refer to existing scientific literature, information from facility assessments, expense reports, and project staff interviews to estimate the health system cost per patient treated.

Our modified societal perspective will include both health system costs (outlined in the paragraph above) and patient costs (as outlined earlier). Health system costs and patient costs will be summed on an individual basis to generate an estimate of the per-patient cost of diagnosis and treatment. This value will be estimated as a mean across all participants providing these data. Health system costs will be divided by the total number of participants at each site. We will report this outcome both by site and by country. Incremental cost-effectiveness ratio, modified societal perspective

QMS Form number: FM-06-02-	CONFIDENTIAL	Page 16 of 26
05/v2.0		-

FIND >>>	Statistical Analysis Plan		
Protocol number:	TB041-3/1-TAN / -MOZ		
Document version:	5.0	Document date:	11-JUL-2023

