This quantity will be estimated as the incremental cost of the intervention (cost of intervention minus cost of standard of care), divided by the incremental effectiveness (i.e., incremental number of people diagnosed and treated in the intervention versus the standard of care). As above, a modified societal perspective will be used for both costs and effectiveness. The cost component of this equation will be estimated as described in the "unit costs" section above; the effectiveness component will be estimated as described for the primary outcome above. We will estimate uncertainty in this quantity using a simulation approach, where we draw independent simulations from the distribution of the primary outcome as inferred from the 95% confidence interval of the primary effectiveness outcome, as well as from the distribution of unit costs based on the empiric distribution of unit costs from our measurements above. We will report 95% uncertainty intervals as the outcomes falling within the smallest area covering 95% of the simulated costs and effectiveness values, plotted on a cost-effectiveness plane. We will perform these analyses separately by country.

BIA and ECEA of TB diagnostic tools.

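### The cost-effectiveness simulation in SAP 4.3 takes effects from a confidence interval but costs, on its plain reading, from the spread between patients, with no joint draw

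*SAP*

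**What the plan says.** SAP 4.3 defines the ICER as incremental cost over incremental number of people diagnosed and treated, with the effect estimated as for the primary outcome. Uncertainty comes from simulation, separately for each country:

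- **Effect:** "where we draw independent simulations from the distribution of the primary outcome as inferred from the 95% confidence interval of the primary effectiveness outcome".
- **Cost:** "as well as from the distribution of unit costs based on the empiric distribution of unit costs from our measurements above".
- **Reported:** the "smallest area covering 95% of the simulated costs and effectiveness values, plotted on a cost-effectiveness plane".

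The unit-cost paragraph just before it describes those measurements. "Health system costs and patient costs will be summed on an individual basis to generate an estimate of the per-patient cost", and then "This value will be estimated as a mean across all participants providing these data". The health-system part is a site average: "Health system costs will be divided by the total number of participants at each site".

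For the primary outcome, SAP 4.2 says "ORs will be estimated by calculating the exponent of the fixed-effect (i.e. arm) coefficients", with Wald intervals. SAP 2.2 states that the ICER itself is not formally tested, although its components are.

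**The concern.** The two axes of the plane would carry different kinds of variation. A confidence interval describes how well an effect is estimated. An empirical distribution of individually summed costs describes how much patients differ from each other. The ICER concerns a difference in means, so its cost axis needs the sampling uncertainty of that difference.

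Two further gaps add to this. Costs include treatment and the effect is people treated, so the two are linked, yet they come from two separately specified distributions. And a ratio-scale interval does not by itself give the distribution of an absolute number treated.

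Protocol section 7 says that the findings should inform policy on use and scale-up. Because the ICER has no formal test, this region is its main statement of uncertainty. If patient heterogeneity dominates the region, it could obscure a cost increase or saving that the data do support.

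**Working it through.** The documents give no figure for the ICER interval. The check takes the effect's standard error from the plan's own sample-size formula and the interview numbers from the documents. Everything else is assumed and varied.

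**1. Reproduce the plan's figure.** Inputs (protocol 13.8, SAP 8): prevalence 12%; sensitivity 89% v 70%; diagnostic loss 2% v 10%; pre-treatment loss 10% v 20%; cluster size 150; within-pair CV 0.25.

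- p_i = 0.12 × 0.89 × 0.98 × 0.90 = 0.0942
- p_c = 0.12 × 0.70 × 0.90 × 0.80 = 0.0605; difference 0.0337
- Variance term = p_i(1−p_i)/150 + p_c(1−p_c)/150 + 0.25²(p_i² + p_c²) = 0.00173
- Pairs = A + 7.849 × 0.00173/0.0337² = A + 11.95

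The protocol's A = 1 gives 12.95, rounded up to the stated 13. (The SAP prints A = 2, which would give 14; that is a separate matter.)

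**2. Effect standard error.** Whole trial, 14 pairs: √(0.00173/14) = 0.0111. Per country, assuming an even split into 7 pairs: √(0.00173/7) = 0.0157, so the planned 95% interval is 0.003 to 0.065.

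**3. Number interviewed per arm and country.** Protocol 9.11 has about 50 per site. Two sites per country give 100, or about 50 per arm. SAP 3.1 has 5–10%. Of about 2,100 per country (4,200/2) that is 105–210, or about 52–105 per arm.

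**4. Cost axis.** The difference of two single draws has SD √(σ_i² + σ_c²). The difference of two means has SE √((σ_i² + σ_c²)D/n), where D = 1 + (m−1)ICC and m = n/7 interviewed per clinic. The ratio is √(n/D).

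| n per arm | ICC 0 | ICC 0.2 |
|---|---|---|
| 50 | √50 = 7.1 | D = 2.23; √(50/2.23) = 4.7 |
| 105 | √105 = 10.2 | D = 3.8; √(105/3.8) = 5.3 |

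The ratio does not depend on the cost CV. It applies to patient costs. Health-system costs are site averages and have no between-patient spread to inflate.

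**5. ICER interval.** Monte Carlo with 400,000 draws, per country: effect normal (0.0337, SE 0.0157); mean costs 100 and 120 in arbitrary units; lognormal patient costs plus a constant health-system part; 50 interviewed per arm; ICC 0.05. Individual-cost draws independent of the effect were compared with draws of the mean, over patient-cost share 25–100%, cost CV 0.5–2 and correlation −0.5 to +0.5.

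- Low end (share 25%, CV 0.5, correlation −0.5): 1.5 times too wide.
- Middle (share 50%, CV 1, correlation 0): −6349 to 9699 against −324 to 3557, 4.1 times.
- High end (share 100%, CV 0.5, correlation +0.5): −6932 to 10298 against −392 to 2194, 6.7 times.

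With zero correlation the range is 1.7 to 5.0.

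**6. Correlation alone.** Costs were drawn correctly from the mean, with patient costs half the total. Treating the draws as independent makes the ICER interval about 1.25–1.5 times too wide if the true correlation is +0.5. If it is −0.5, the interval is only about 0.75–0.8 of the right width.

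**7. Scale.** The planning proportions give an odds ratio of (0.0942/0.9058)/(0.0605/0.9395) = 1.62. The same odds ratio implies a risk difference of 0.018, 0.033 or 0.061 at control proportions of 3%, 6% or 12%. The SAP does not state the baseline or the conversion.

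**The case against.** The strongest reply is that the SAP never says that single patients' costs are drawn. The unit cost is defined as a mean, and a distribution based on the empirical one could be a bootstrap of that mean. In that case the cost factor is 1, and only the joint-draw and scale points remain. This stands in part. A reader might infer that individual draws are the SAP's stated method and that the reported interval is simply several times too wide. The documents do not support that: the draw level is not explicit, the effect axis is unaffected, and the ICER factor can be as low as 1.5. But nothing mentions a standard error of cost, a bootstrap or resampling of clinics, so a programmer following the text literally would draw individual costs.

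Other replies also carry weight:

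- **Health-system costs.** Giving the whole cost individual spread exaggerates the effect. With assumed means of 35 v 25, CV 1 and 100 interviewed per arm, the simulated probability that Truenat costs less is 39% if all cost varies by patient. It is 23% if patient costs are half the total and 9% if they are a quarter.
- **Independence.** A reader might infer that independent draws always widen the interval. They do not, and the documents do not fix the sign. Treatment costs push the correlation up. Patient costs counted only until treatment starts could push it down. The word may also mean only independent replicates, but two separate distributions still give zero correlation.
- **Scale.** SAP 2.1 promises intervals for numbers and proportions, and SAP 4.2 adds a Poisson count model. This softens the mismatch. However, the only stated effect extraction exponentiates the arm coefficients, which gives ratios.
- **Consequence.** Patient costs have their own mean-difference hypothesis in SAP 2.2, so a clear patient-cost difference would still be visible there.

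**Conclusion.** The point holds and should be corrected before the analysis. Followed on its plain reading, SAP 4.3 combines between-patient spread in cost with estimation uncertainty in effect, so the result is not a valid 95% region for an ICER of means. Under that reading the patient-cost axis is 4.7–10.2 times too wide per country, and the ICER interval about 1.5–6.7 times.

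The cost-axis range rests on 50–105 interviewed per arm and an assumed cost ICC of 0–0.2. The ICER range rests also on the assumed cost CV, patient-cost share and correlation, and on an even split of clinics and participants. None of these cost inputs is in the documents. The missing joint draw and the unstated conversion from ratio to absolute difference remain on either reading, and the first can err in either direction. The ICER is a secondary, untested outcome, so the trial's primary conclusion does not depend on this.

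**What to change.** Replace the simulation with draws, by country, from the joint sampling distribution of the difference in mean cost per enrolled participant and the risk difference. Define the ICER as the first divided by the second. Two routes are suitable:

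- a bivariate normal with a cluster-robust covariance and a small-sample correction; or
- a bootstrap of whole clinics within arm and country, with a small-sample variance correction. Each replicate computes the risk difference from all participants and the mean patient cost from the interviewed subsample.

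Do not resample within strata. With 28 clinics, two arms and 6–8 strata, a cell holds 28/16 = 1.75 to 28/12 = 2.3 clinics. A bootstrap of k clinics recovers (k−1)/k of the between-clinic variance, so cells of two give a standard error √(1/2) = 0.71 of the right size and cells of one contribute nothing. Seven clinics per arm and country give √(6/7) = 0.93, which the small-sample correction can repair.

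Give site-level and literature-based health-system costs their own stated distributions, because patient resampling cannot supply them. If a bootstrap of the mean was intended all along, say so and add the joint draw and the risk-difference definition.

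The cost is SAP wording and a little more programming, with no new data.

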4.4 Analysis of missing data patterns

Additional exploratory analyses will be performed to investigate any pattern in missing data. If the outcomes will be missing at random or missing completely at random the above longitudinal data models or clustered data models considering the mixed effect regression under maximum likelihood estimation will be appropriate. Missing at random can be tested by regression the binary outcome of missing or not, with independent variables as the other covariates in the model. If this binary outcome of missingness is associated with the outcome of interest in the model framework, we expect to have the Missing Not at Random in our outcome data. In case it is dependent on other covariates but not the outcome of interest, we are likely to have Missing at Random. In the event of patterns for missing data being not random, the results of the regression will be reported and a detailed plan will be developed to assess the association between the missingness and each covariate. Depending on the results of the analyses, sources of bias will be determined and documented.

5 Baseline descriptive statistics

Descriptive statistics tables will be generated to summarize the characteristics of the participants in the PP, PPM, MITT and ITT populations. The number of participants included and excluded will be reported, overall and for each arm within the hierarchy of each cluster and site.

Among the included participants, outcomes of interest as described above as well as covariates such as sex, age (continuous and categorical as age groups defined as: 18-30, 31-40, 41-50, >50), HIV status, site (i.e. 4 different institutions), country setting (Urban, Rural, Peri-rural), RIF resistance, asset index and the variables that are used for determining the asset index will be summarized.

The summary of measurements and descriptive statistics will also be presented for the overall PP population and at the cluster level (i.e. clinic-based characteristics) for clinics in each of the study arms. The outcomes of interest are, number of patients (size of the unit), number of individuals tested positive, and number of individuals who started treatment, number of patients with presumptive TB seen, number of patients by enrolment period, number of staff at the clinic, time to TB diagnosis, time to TB treatment.

Results will be reported in both absolute numbers (e.g. number of subjects in a group) and the proportion, or summarized by mean, median, standard deviation, minimum, maximum and quartiles. Differences in the groups of Intervention and SOC will be tested by Chi² Test or Fisher exact test for categorical outcomes, and Kruskal-Wallis test, t- test, ANOVA or Wilcoxon signed rank test for continuous data depending on whether parametric or non-parametric tests are appropriate for the observed data.

QMS Form number: FM-06-02-	CONFIDENTIAL	Page 18 of 26
05/v2.0		-

FIND >>>	Statistical Analysis Plan				
Protocol number:	TB041-3/1-TAN / -MOZ				
Document version:	5.0	Document date:	11-JUL-2023		

6 Additional sub-group analyses

All primary and secondary endpoints will be evaluated separately by sex and gender (if the information is available), HIV status, site, country, asset index, and age categories (as given in Section 5).

7 Exploratory analyses

Protocol Deviation

A proportion of participants were contacted outside of their contact window. 808 participants were affected concerning the V2, and 40 participants were affected concerning the V3. For participants where V2 was not done, V3 was also not done.

Since the data was collected retrospectively, a bias might have occurred since the participants may not recall exactly their status of treatment during the actual Day 7 and Day 60. To overcome this bias.

- 1) A list with IDs of all affected participants was formed by the data manager (15/03/2023 data extract) and reported to national IRB ref: 173/CNBS/23, and this is defined as the MPP population,
- 2) The data that was entered retrospectively was crosschecked with the TB, treatment registry at the clinic (~50 registries) to make sure the treatment initiation data was not misrecorded.
- 3) Descriptive statistics will be performed to describe the number and the percentage of the effected participants (V2, V3, and both) in both arms in the PPM population,
- 4) Descriptive statistics will be performed to describe the number and the percentage of the effected participants for the treatment outcome at day 7. Chi² test will be performed to assess the statistical significance of the difference between the PP and PPM populations. In case of statistical significance, all the models in the study will be adjusted for the deviation (TRUE/FALSE).
- 5) A survival analysis will be performed on PP (i.e. participants without the protocol deviation) and in PPM population on time to treatment initiation to explore the possibility of bias.

Other measures can be taken depending on the distribution of the outcome related data

8 Sample size

For the purpose of sample size estimation, a matched design is considered which is known to have a similar power in the range of number of clusters per treatment arm similar to this study (~15). Sample size calculations were based on 972 scenarios using the following ranges of assumptions:

- TB prevalence: 12%, 16%, 20%
- Sensitivity for intervention group: 89%
- Sensitivity for control group: 70%, 75%, 80%
- Diagnostic LTFU intervention arm: 2%
- Diagnostic LTFU control arm: 5%, 10%

QMS Form number: FM-06-02-	CONFIDENTIAL	Page 19 of 26
05/v2.0		-

FIND >>>	Statistical Analysis Plan			
Protocol number:	TB041-3/1-TAN / -MOZ			
Document version:	5.0	Document date:	11-JUL-2023	

- Pre-treatment LTFU intervention arm: 8%, 10%, 12%
- Pre-treatment LTFU control arm: 16%, 20%, 24%¹
- Cluster size CS 100, 125, 150, 200 (cluster sizes are regarded as average values of a distribution of cluster sizes).
- Within pair coefficient variation CV_m: 0.25 according recommendation in case of missing information given in³²
- Alpha-level $\alpha = 0.05$
- Power: 80% ($\beta = 0.2$)

From the prevalence, sensitivity and LTFUs in the diagnostics the proportions p of treated patients is derived ($p = prev \cdot sens \cdot (1 - LTFU_{diag}) \cdot (1 - LTFU_{pre-ther})$ for each of intervention and control arm ($\rightarrow p_i, p_c$).

The number of cluster pairs N_{cp} is calculated according to the following formula [Hayes RJ, Moulton LH 2017]:

$$N_{cp} = A + (z_{\alpha/2} + z_{\beta})^{2} \frac{p_{i}(1 - p_{i})/CS + p_{c}(1 - p_{c})/CS + CV_{m}^{2}(p_{i}^{2} + p_{c}^{2})}{(p_{i} - p_{c})^{2}}$$

whereby the result is rounded up to the next whole number, with A=2, z= quantile of normal distribution.

The following scenarios have been selected according to feasibility and mid-range choice of the ranges presented above are shown in the tabulation below. Colours vary with cluster size and prevalence. The finally selected scenario is described below in red.

Cluster size	Prevalence	Sensitivity control	diagn. LTFU control (diagn. LTFU for intervention: 0.02)		pre-trt. LTFU control	success proportion intervention	success proportion control	number of cluster pairs	Number of clusters	Number of patients
100	16%	70%	10%	10%	20%	13%	8%	14	28	2800
100	12%	70%	10%	8%	20%	10%	6%	15	30	3000
100	12%	70%	10%	10%	20%	9%	6%	17	34	3400
100	12%	70%	10%	12%	20%	9%	6%	18	36	3600
150	12%	70%	10%	10%	20%	9%	6%	13	26	3900

QMS Form number: FM-06-02-	CONFIDENTIAL	Page 20 of 26
05/v2.0		

FIND >>>	Statistical Analysis Plan				
Protocol number:	TB041-3/1-TAN / -MOZ				
Document version:	5.0	Document date:	11-JUL-2023		

150	16%	70%	5%	10%	20%	13%	9%	14	28	4200
150	16%	70%	10%	10%	20%	13%	8%	12	24	3600
200	12%	70%	10%	10%	20%	9%	6%	12	24	4800
200	16%	70%	5%	10%	20%	13%	9%	13	26	5200
200	16%	75%	10%	10%	20%	13%	9%	14	28	5600

Applying an alpha-level of 0.05, a power of 80%, 12% prevalence, diagnostic LTFU-rates of 10% (control), 10% (pre-treatment intervention), 20% (pre-treatment control), a cluster size of 150 and a within-pair coefficient of variation (default value 0.25), the results bring a total of 13 cluster pairs (3900 patients). In order to address uncertainty, 1 additional cluster pair will be added, bringing the total to 14 cluster-pairs (28 clinics, 4200 patients) to be included in the trial. If based on what will be observed in the initial setup period, smaller than average cluster sizes are expected, more sites will need to be included in the trial in order to match the total sample size.

Randomisation process

Taking into account the strata, a restricted randomisation approach [Hayes RJ, Moulton LH (2017): Cluster Randomized Trials, 2nd Ed, Chapter 6, Chapman & Hall/CRC Press] will be applied to achieve balance between the treatment arms. Among all possible distributions of clusters within strata, those, which are balanced due to specific stratification variables, will be used. This stratification will be by site and size of clinic. In addition, the same or similar number of clusters (max. difference=1) should be allocated to each treatment arm within each stratum. The number of strata per site will depend on heterogeneity of the sizes of the clinics as established during setup period. Typically, one or two strata per site will be established. A total of 6-8 strata are expected but might be increased dependent on the results of the setup period. All possible allocations will be established, whereby balance criteria covering a pre-specified variability of the stratification variables within a stratum will be applied. The size of the clinic (number of TB patients within a 2-month period) should not differ more than 20%. The allocations will be checked for validity, especially whether the clusters are spread independently among the allocations. If this is not the case, the balance criteria will be chosen less restrictive. If the number of allocations exceeds 10000, a subsample is drawn. Finally, one of the allocations will be chosen randomly.

Bias reduction

The objective of the trial is to assess Truenat platform in clinical care. The use of Truenat does not allow blinding of clinicians and participants in this trial. The trial-related procedures will be embedded into the routine practice at the primary-level facility. Data analysts will be blinded to intervention allocation.

Randomisation takes place on a cluster level rather than for the individual patients to avoid contamination between the arms within a health facility. Since clinics will be relatively far apart, contamination is unlikely.

Due to the result availability on the same day as the testing in the intervention clinics, the recruitment rate in intervention clinics may be faster than the control clinics. To minimize the

QMS Form number: FM-06-02-	CONFIDENTIAL	Page 21 of 26
05/v2.0		-

FIND	Statistical Analysis Plan			
Protocol number:	TB041-3/1-TAN / -MOZ			
Document version:	5.0	Document date:	11-JUL-2023	

potential bias resulting from this, we will monitor the recruitment rate (i.e. percentage of interviewed participants/target enrolment by arm) continuously. If the difference between the control and the intervention arms exceeds 5% we will investigate enrolment within individual clinics to determine if the recruitment in one or a few clinics constitutes the main cause of difference. If this is the case, the sponsor will contact the clinic to determine the source of bias. Any identified biases that are not related to participant safety will be documented in a note to file.

We will contact participants for the seven and 60-day outcomes by telephone to investigate whether more diagnostics available at the level of the primary health care facility (without the need to refer samples) result in more microbiologically confirmed cases and more rapid treatment initiation. Losses to follow- up pre-diagnosis and during treatment are among the endpoints of the trial. There is a chance that contacting the participants after seven and 60 days may influence their treatment seeking behaviour in the control arm and reduce loss to follow-up. By keeping contact with trial participants to a minimum, (i.e. three time points), we hope to limit the impact on treatment seeking behaviour.

9 Statistical software

The analysis will be performed using the R statistical language (version 4.2.2 or higher). The scripts used for the entire analysis and the generation of the results will be provided to allow the reproducibility of the results.

10 References

- 1. Verbeke G. and Molenberghs G. (2000) `Linear mixed models for longitudinal data,' Springer Series in Statistics, Springer-Verlag, New-York, ISBN 978-1-4419-0299-3.
- 3. Molenberghs G. and Verbeke G. (2005) `Models for discrete longitudinal data,' Springer Series in Statistics, Springer-Verlag, New-York, ISBN 0-387-25144-8.

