13. STATISTICAL CONSIDERATIONS

13.1 Populations to be analyzed

Intent-to treat (ITT) population: The ITT population will consist of all enrolled patients in the groups to which randomly assigned to intervention and controls. Patients with missing outcome data at days 7 and 60 will be assumed to not have started treatment.

Per-Protocol (PP) population: The PP population will consist of all patients who fulfil the protocol in the terms of eligibility, interventions, and outcome assessment without any major protocol deviation.

The Statistical Analysis Plan (SAP) will define the criteria for the exclusion of patients from any of the above-mentioned analysis populations and will be finalized prior to database lock. The SAP will also provide a detailed summary of the analysis methodology for each of the outcomes of the trial.

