4.1 General approach

All analyses will be performed on the MITT and PP populations. Because there was a protocol deviation (i.e. participants with missing V2 or V3), the potential difference in the primary outcome between the two populations will be explored as described in *Section 7.0*.

All analyses (i.e. generalized linear models and proportional hazards models) will take into account the effect of the clusters using a mixed model approach, introducing a random intercept for each cluster. Details of the models for each outcome are given in the sections below.

For all statistical tests, alpha will be set to 0.05 for rejecting the null hypothesis. Since multiple comparisons will be performed, p-values will be adjusted using Benjamini-Hochberg method.

The proportion of observations with missing values will be summarised for all outcome variables. Missing and invalid data will not be imputed. Baseline measures will be reported for individuals with missing data on an outcome of interest, including those who withdraw or are lost to follow-up. For each analysis, the baseline measures (demographic and laboratory data) will be compared between participants with complete and incomplete data using T-Tests or Chi² tests, for continuous or categorical variables respectively.

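### SAP 4.4 infers MAR or MNAR from an association that cannot be estimated where the endpoint is missing from every source, so it cannot support calling the mixed models appropriate

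*SAP*

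**What the plan says.** SAP 4.4 is introduced as additional exploratory work. It states that "Missing at random can be tested by regression the binary outcome of missing or not", with the other model covariates as predictors. Two sentences then interpret the mechanism. MNAR is expected "If this binary outcome of missingness is associated with the outcome of interest in the model framework". The alternative reads: "In case it is dependent on other covariates but not the outcome of interest, we are likely to have Missing at Random". Under MAR or missing completely at random, "the mixed effect regression under maximum likelihood estimation will be appropriate". Should a systematic pattern emerge, "the results of the regression will be reported and a detailed plan will be developed to assess the association between the missingness and each covariate", and sources of bias are to be documented. No delta, tipping-point or best/worst-case analysis is named.

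SAP 4.1 sets the handling that actually applies: "Missing and invalid data will not be imputed" and "All analyses will be performed on the MITT and PP populations". SAP 3.2 limits MITT to participants with Visit 2 or Visit 3 data. It also defines an ITT set, without a rule for missing outcomes; SAP 5 uses that set for descriptive tables.

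Protocol 13.1 does give a rule for the ITT population: "Patients with missing outcome data at days 7 and 60 will be assumed to not have started treatment".

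**The concern.** MAR and MNAR differ in whether, given what is observed, missingness still depends on the unobserved value. Data that lack the value cannot settle that. A regression of missingness on covariates can show that missingness varies with age, HIV status or arm. It cannot show that nothing further depends on the outcome. A reader of the report could therefore be told that the models are appropriate on evidence that does not bear on the question.

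Informative missingness is plausible here. Protocol 4 and 5.2 describe treatment start as depending on results coming back and the patient returning, so people who cannot be reached may be those who never returned. Conversely, the follow-up interviews ask about other health care providers, so an unreached participant may have started elsewhere without appearing in the clinic's register. If the balance of these differs by arm, the observed-case comparison is biased, in a direction that the data do not reveal.

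**Working it through.** **1. Can the association be estimated?** Let R = 1 if the endpoint is missing from all sources, and Y = started treatment with microbiological confirmation by day 7. Where R = 0, Y is known. Where R = 1, Y is unknown. Comparing Y between R = 0 and R = 1 needs values that do not exist. What can be estimated is R against covariates and, as a partial check, missing Visit 2 against treatment starts recorded in the register or worksheet.

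**2. What analysis results?** Each participant contributes one binary primary endpoint. A likelihood mixed model without imputation then uses only participants with that endpoint observed. This follows from SAP 4.1 and 3.2, whatever 4.4 finds.

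**3. Event rates.** From Protocol 13.8 and SAP 8 (selected scenario), p = prevalence × sensitivity × (1 − diagnostic LTFU) × (1 − pre-treatment LTFU):
- p_i = 0.12 × 0.89 × 0.98 × 0.90 = 0.0942
- p_c = 0.12 × 0.70 × 0.90 × 0.80 = 0.0605
- difference 3.4 points; odds ratio 1.615

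SAP 4.4 states no figure of its own. As a check on these rates, the plan's formula with cluster size 150 and CV 0.25 gives A + 7.849 × (0.000569 + 0.000379 + 0.000783) / 0.001137 = A + 11.95. With the protocol's A = 1 this is 12.95, rounded up to the stated 13 pairs. (The A = 2 printed in SAP 8 would give 14; that is a separate matter.)

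**4. Illustration.** Missing fractions m_i (intervention) and m_c (control) are assumptions. The observed rates are held at p_i and p_c.

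Missing = not started: difference = p_i(1 − m_i) − p_c(1 − m_c).

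Missing controls start at 2p_c and missing intervention participants do not start: difference = p_i(1 − m_i) − p_c(1 + m_c).

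| m_i, m_c | Not started: points (OR) | Controls at 2p_c: points (OR) |
|---|---|---|
| 5%, 5% | 3.2 (1.61) | 2.6 (1.45) |
| 5%, 10% | 3.5 (1.71) | 2.3 (1.38) |
| 10%, 5% | 2.7 (1.52) | 2.1 (1.37) |
| 10%, 10% | 3.0 (1.61) | 1.8 (1.30) |

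All eight cells fit the same observed data. If every missing participant starts in one arm and none in the other, the odds ratio can lie anywhere from 0.82 to 2.66 at 5% missing in each arm and from 0.51 to 3.94 at 10%.

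**5. What the covariate regression can see.** Suppose the full-data rates are p_i and p_c, 10% are missing in each arm, and 30% of control starters are missing. The observed control rate is 0.0605 × 0.70 / 0.90 = 0.0470, and the observed-case odds ratio is 2.11 against a full-data 1.61. In 400 simulated trials of 2,100 per arm (no clustering), regressing missingness on arm and one covariate flagged either in 8% of runs, about what two 5% tests give by chance. The scenario is deliberately strong: it implies an 18% start rate among missing controls (0.30 × 0.0605 / 0.10). It shows what the regression can miss; it is not a forecast.

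**The case against.** Several points on the other side stand.

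- A reader might infer that the SAP puts the unobserved outcome into the regression. It does not: the predictors are covariates, and the outcome enters only in the two sentences of interpretation.
- A reader might infer that 4.4 is what authorises an observed-case analysis. The documents do not support that. Section 4.4 is exploratory, SAP 4.1 fixes no imputation regardless, and the primary model in SAP 4.2 does not branch on 4.4. Deleting the rule alone would leave the primary estimate unchanged.
- A reader might infer that the rule can never point to MNAR. That is too absolute. Protocol Table 1 lists the register and worksheet as sources for the primary endpoint, Protocol 9.8 has the study and TB registers compared weekly, and SAP 7 cross-checks retrospective entries. Missing interviews can be compared with recorded starts. The limitation is strict only for participants missing from every source, a fraction that the documents do not give.
- The SAP is not silent on missing data: 4.1 summarises it for every outcome and compares baseline measures between complete and incomplete cases.
- If unreached people simply did not start, and equally often in both arms, the odds ratio hardly moves. With 5% missing in intervention and 10% in control, the observed-case result is the more conservative one.

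None of this makes the MAR/MNAR inference valid, and the SAP names no sensitivity analysis to replace it.

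**Conclusion.** The point holds in this form: SAP 4.4 cannot establish MAR for participants with no endpoint from any source, and should not be used to declare the mixed models appropriate. If MAR given the model covariates happened to be true, the analysis would be valid; the error is in claiming to have tested it. Alongside this, the only explicit assumption about missing endpoints, in Protocol 13.1, is not carried into the SAP.

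At 5% to 10% missing per arm, the planned 3.4 points become 2.7 to 3.5 under missing = not started, and 1.8 to 2.6 if missing controls start at twice the control rate and missing intervention participants do not start. Both the missing fractions and the start rates among the missing are assumptions. Equal missingness with missing = not started gives an odds ratio of about 1.61, so the exposure is to missingness, or start rates among the missing, that differ by arm.

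A reader might take the 808 participants with a Visit 2 deviation (19.2% of the 4,200 target) as the missing rate. The documents do not support that: SAP 7 describes them as contacted outside the window, with data collected retrospectively and checked against treatment registries.

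**What to change.** In the SAP:

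1. Keep the regression of missingness on covariates in 4.4 as description, and delete the MAR/MNAR inference and the statement that the models are then appropriate.
2. Run the Protocol 13.1 ITT analysis, counting missing as not started, after reconciling interviews with the TB register and outcome worksheet. State when an endpoint counts as missing after that reconciliation.
3. Prespecify a tipping-point analysis that varies the start probability among missing participants separately by arm, using the same clustered model, and report where the conclusion changes.
4. Report the number with no endpoint from any source, by arm and clinic.

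The cost is SAP wording and a short sensitivity script. No new data are needed.
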